MEDICAL PROTOCOL (HRP-590)

PROTOCOL TITLE: Capillary Refill Time Measurement Utilizing Mobile Application (Cap App) in Children
 VERSION DATE: 10/27/2022

ANCILLARY REVIEWS

DO NOT DELETE. Submit the completed checklist below with your protocol.

| Which ancillary reviews do I need and when do I need them? Refer to HRP-309 for more information about these ancillary reviews. | | | |
|-----------------------------------------------------------------------------------------------------------------------------------------------------------|-----------------------------------------------------------------------------------------------------------------------------------------|-----------------------------------------------------------------------------------------------------------------------------------------------------------------------------------------------------------------------------------------------------------------------|------------------------------------------------------------------------|
| Select yes or no | Does your study... | If yes... | Impact on IRB Review |
|  Yes  No | Include Gillette resources, staff or locations | Gillette Scientific review and Gillette Research Administration approval is required. Contact: [contact] | Required prior to IRB submission |
|  Yes  No | Involve Epic, or Fairview patients, staff, locations, or resources? | The Fairview ancillary review will be assigned to your study by IRB staff Contact: [contact] | Approval must be received prior to IRB committee/designated review. |
|  Yes  No | Include evaluation of drugs, devices, biologics, tobacco, or dietary supplements or data subject to FDA inspection? | The regulatory ancillary review will be assigned to your study by IRB staff Contact: [contact] See: https://policy.umn.edu/research/indide | Consider seeking approval prior to IRB submission. |
|  Yes  No | Require Scientific Review? Not sure? See guidance in the Investigator Manual (HRP-103). | Documentation of scientific merit must be provided. Contact: [contact] | |
|  Yes  No | Relate to cancer patients, cancer treatments, cancer screening/prevention, or tobacco? | Complete the CPRC application process. Contact: [contact] | |
|  Yes  No | Include the use of radiation? (x-ray imaging, radiopharmaceuticals, external beam or brachytherapy) | Complete the AURPC Human Use Application and follow instructions on the form for submission to the AURPC committee. Contact: [contact] | Approval from these committees must be received prior to IRB approval; |
|  Yes  No | Use the Center for Magnetic Resonance Research (CMRR) or MR from Masonic Institute for the Developing Brain (MIDB) as a study location? | Complete the CMRR pre-IRB ancillary review Contact: [contact] | These groups |

MEDICAL PROTOCOL (HRP-590)

PROTOCOL TITLE: Capillary Refill Time Measurement Utilizing Mobile Application (Cap App) in Children
 VERSION DATE: 10/27/2022

| | | | |
|------------------------------------------------------------------------|-------------------------------------------------------------------------------------------------------------------|-----------------------------------------------------------------------------------------------------------------------------------------------------------------------------------------------|--------------------------------------------------------------------------------------------------------------------------------|
|  Yes  No | Include the use of recombinant or synthetic nucleic acids, toxins, or infectious agents? | Complete the IBC application via eprotocol.umn.edu | each have their own application process. |
|  Yes  No | Include the use of human fetal tissue, human embryos, or embryonic stem cells? | Contact OBAO for submission instructions and guidance | |
|  Yes  No | Include PHI or are you requesting a HIPAA waiver? | If yes, HIPCO will conduct a review of this protocol. Contact: [contact] | |

- IND/IDE - Investigational New Drug/Investigational Device Exemption
- OIT - Office of Information Technology
- FDA - Food and Drug Administration
- IRB - Institutional Review Board
- AE - Adverse Event
- LAR - Legal Adult Representative
- DUA - Data Use Agreement
- NSR - Non Significant Risk

MEDICAL PROTOCOL (HRP-590)

PROTOCOL TITLE: Capillary Refill Time Measurement Utilizing Mobile Application (Cap App) in Children
VERSION DATE: 10/27/2022

1.0 Objectives

1.1 Purpose: To determine the accuracy and precision of capillary refill time measurement using a mobile health application (Cap App) in a healthy pediatric population. This will be a cross-sectional study measuring the capillary refill time in a healthy pediatric population using both the Cap App and two additional manual methods which will serve as the comparison.

2.0 Background

1.1 Significance of Research Question/Purpose: A prolonged CRT is used to determine inadequate skin perfusion (1). It is a subjective physical exam finding which can be used to aid in the diagnosis of shock from any cause, such as hypovolemic (dehydration), septic, or hemorrhagic. This quick test which can be performed in any medical setting is vital to the assessment of circulation in children as recommended by the Pediatric Advanced Life Support course (2). Despite its clinical importance, there is low interobserver agreement among providers performing this routine clinical test (3). Additionally, Capillary refill time (CRT) is the time it takes for blood to return to tissue (on the fingertip, for instance) blanched by pressure. There is significant age and sex variation of normal CRT amongst otherwise healthy patients (1). The subjective nature of the CRT also limits the utility and improved clinical detail that might be obtained by quantifying the CRT more precisely. As currently employed, the clinician identifies the CRT as either normal or prolonged. This binary classification of CRT may be limiting its clinical usefulness. For instance, improved access to precise measurement of CRT may help improve the accuracy of the level of dehydration (mild/moderate/severe) and, thereby, reduce unnecessary emergency department (ED) visits and/or intravenous (IV) treatments. In addition, CRT has been utilized to assess, diagnose, or monitor many medical conditions in the pediatric population, such as hypovolemic, hemorrhagic, and septic shock.

The Cap App is a mobile smartphone application that we developed to measure CRT. It utilizes photoplethysmography (PPG) to calculate CRT. Previous research has shown that PPG — a technique that optically measures the blood volume changes in the microvascular bed of tissue via light absorption — can be achieved using the combination of a smartphone's flash and camera. To use such systems, a patient simply covers the flash and camera simultaneously using their finger. The amount of light that is reflected to the camera depends on the presence of two components: tissue, which remains constant over time; and blood, which varies over time. Therefore, the camera records and subsequently analyzes relative color changes to reproduce the PPG waveform, irrespective of a person's skin tone. This technique has been used to estimate heart rate (7), pulse-transit time (8), and even hemoglobin (9), and we have applied this approach in Cap App to measure capillary refill time.

MEDICAL PROTOCOL (HRP-590)

PROTOCOL TITLE: Capillary Refill Time Measurement Utilizing Mobile Application (Cap App) in Children

VERSION DATE: 10/27/2022

Beyond making the capillary refill time assessment more precise, Cap App also makes the procedure more repeatable by ensuring that sufficient blanching has been achieved by using a combination of the PPG waveform and motion sensing. As the patient presses their finger against the camera, the phone vibrates, and its motion sensor measures how much the phone vibrates; harder pressure dampens the phone's vibration and causes a weaker signal (10). As blood leaves the fingertip, the amplitude of the PPG signal diminishes and eventually stabilizes to a brighter color due to blanching.

Improved access to precise measurement of capillary refill time will help expand the capabilities of experienced providers who are treating patients remotely through telehealth or less experienced providers treating patients in remote locations. This is especially important in low-resource settings or regions remote from specialty centers where providers may not be as experienced in the care of children. Triaging care for conditions such as pediatric dehydration is challenging due to lack of resources, especially in developing countries. However, even in well-developed nations, access to specialized care for pediatric patients is still lacking. Pediatric specialized care in the United States is largely regionalized. Most seriously ill children present first to community hospitals where resources and expertise to treat these children may be limited. In fact, more than 90 percent of emergency department visits for children in the United States are to non-specialty facilities (11). Admission rates for large specialty pediatric hospitals are 2-4 times larger than general emergency departments suggesting that the majority of providers caring for children have limited experience in treating higher acuity pediatric conditions (12). Additionally, in the setting of rising health care costs, many parents and other non-professional caregivers are increasingly seeking health information from non-traditional sources such as mobile smartphones.

- 2.1 Preliminary Data: A pilot study is ongoing on healthy adult volunteers. This study is not yet published in a peer-reviewed journal. The study's main objective is to compare CRT measured from Cap App versus manual visual assessment under differing temperature controls. The study has enrolled 19 participants, age 20-34; 9 female, 10 male. There is some variance in skin tone. We controlled for 5 temperature conditions (30°C, 27.5°C, 25°C, 22.5°C, 20°C) utilizing an ice bath to determine variance of CRT measurement under progressively colder temperatures. The results show that Cap App measures a longer CRT with greater variance in relation to the colder temperatures. It tends to overestimate CRT for darker skin tones. Overall, CRT is longer for Cap App than for a correlated, manual CRT measurement.
- 2.2 Existing Literature: Capillary refill has been utilized to assess, diagnose, or monitor many medical conditions in the pediatric population, such as hypovolemic and septic shock. Dehydration is one example of hypovolemic shock. The diagnosis of

MEDICAL PROTOCOL (HRP-590)

PROTOCOL TITLE: Capillary Refill Time Measurement Utilizing Mobile Application (Cap App) in Children

VERSION DATE: 10/27/2022

pediatric dehydration is largely based on clinical findings. There have been multiple clinical dehydration scoring systems developed to assess for dehydration in pediatric patients, but none are particularly accurate at differentiating levels of severity (4). Capillary refill has been shown to be the best individual clinical predictor of acute dehydration in children (5). Previous research has shown that video recording of capillary refill time is a promising tool to diagnose dehydration in children. Video computation of capillary refill time has been shown to be more accurate at diagnosing significant dehydration in children than overall clinical assessment by trained pediatric specialists (6). Improved access to precise measurement of capillary refill time may help improve the accuracy of the level of dehydration (mild/moderate/severe) and, thereby, reduce unnecessary ED visits and IV treatments. Our aim with this study is to establish normative values of capillary refill as measured by the Cap App so that we may utilize its accuracy to improve the detection of peripheral perfusion abnormalities in conditions such as dehydration.

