3.0 Study Endpoints/Events/Outcomes

- 3.1 Primary Endpoint/Event/Outcome: Determining the accuracy and precision of a mobile health application (Cap App) to measure CRT in an otherwise healthy pediatric patient population.
- 3.2 Secondary Endpoint(s)/Event(s)/Outcome(s): To establish normal values of CRT via Cap App for healthy children of varying age ranges, determine if subject characteristics such as skin tone, skin temperature, sex, or age affect the CRT measured via the Cap App, and determine if the CRT measured via the Cap App correlates to the manual measurement of CRT in healthy children at varying age ranges.

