4.0 Study Intervention(s)/Investigational Agent(s)

- 1.2 **Description:** Cap App – mobile smartphone application used to measure CRT. The CapApp is a smartphone mobile application created through a partnership with the University of Washington, The University of Toronto, and The University of Minnesota. Management of the application will primarily be the responsibility of The University of Washington Ubiquitous Computing Lab led by [name] and PhD candidate, [name]. Oversight of the project will be from The University of Toronto Assistant Professor of Computer Science, [name]. A standard Android smartphone running a custom smartphone application will be used for collecting fingertip videos, motion data, demographics (e.g., age, sex, temperature), and skin tone using the Fitzpatrick skin color scale. The app will start up and allow the user to enter a study ID and age, sex, race, skin tone, skin temperature, room temperature, core temperature, weight, vital signs (heart rate, blood pressure) and any underlying diagnosis. No other identifying information will be stored, including date of birth, name, audio, or fingerprint. The user is asked to place their right index finger on the

MEDICAL PROTOCOL (HRP-590)

PROTOCOL TITLE: Capillary Refill Time Measurement Utilizing Mobile Application (Cap App) in Children
VERSION DATE: 10/27/2022

front camera. Once the app confirms that the finger is correctly placed, it asks the user to apply pressure against the phone. When the app detects whether the user is applying enough pressure for the specified time, it asks the user to relax the pressure. A function to notate any required assistance for the child in pressing on the smartphone to measure the capillary refill will also be noted. This will be needed especially for younger children and infants as it may cause a difference in how to interpret the results of the measurement. The app collects accelerometer/gyroscope data and video recording of the fingertip. The fingertip recording will not collect fingerprint identification information. The collected data will be uploaded to the cloud server on a secure data storage platform, Box.

The device, as used in this study protocol, does not meet the criteria of a serious risk device under 21 CFR 812.3(m) and therefore is a non-significant risk (NSR) device. The device meets the criteria of a NSR-IDE for the following reasons:

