5.0 Procedures Involved

5.1 Study Design: The study design will be a cross-sectional study. The observation will be to collect the CRT from a population of healthy pediatric participants. Participants who meet the inclusion criteria will have their CRT measured using both the manual measurement (to include both human and computer annotation) and mobile health application (Cap App).

Study Procedures: **Cap App CRT measurement:** Children will be placed in a seated position, and their hand resting on a table top in a resting position. The research assistant will use a smartphone with the mobile health application (Cap App) to measure the CRT. The phone will be placed on a tabletop with the front facing camera face up. The subject's index fingertip will be placed onto the camera of the smartphone with minimal pressure. The finger will then be pressed firmly against the camera for a total of 5 seconds and then released from firm pressure while still contacting the camera with instructions from the Cap App. The research assistant then presses "stop" on the Cap App device. The Cap App will then measure the amount of time it takes for blood to refill the capillary bed as evidenced by the signal return to normal of light shining on the capillary bed. This measurement will be kept blinded to the researcher and be uploaded to a secure web-based cloud server, Box, for analysis. To establish the reproducibility of the index test (or the ability of the test to be accurately replicated), the CRT will be repeated at least twice on the index fingertip with at least 15 seconds between tests, and twice on the index finger of the opposite hand, all within 30 to 60 seconds of each other.

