Manual CRT measurement: Children will be placed in a seated position with their hand raised slightly above the level of the heart on a table. A tripod will be set up for the smartphone to video record the capillary refill test by facing the table from the top. The recording will begin, and audio will not be recorded. The research assistant will compress the index finger of the participant for 5 seconds with transparent plastic and then release the pressure, after which the plastic will be removed from the field of view of the camera. The camera recording will then be stopped once the research assistant has determined the color has returned to its original color. To establish the reproducibility of the index test (or the ability of the test to be accurately replicated), the CRT will be repeated at least twice on 1 fingertip with at least 15 seconds between tests, and twice on the index finger of the opposite hand, all within 30 to 60 seconds of each other. The video, without audio, will be stored in the University of Minnesota's secure online storage platform, Box. For analysis the research study team will complete the following:

- Human annotation from manual CRT measurement: The video will be annotated blindly by a separate research team member than the one who performs the CRT manual measurement. The CRT will be measured as the

MEDICAL PROTOCOL (HRP-590)

PROTOCOL TITLE: Capillary Refill Time Measurement Utilizing Mobile Application (Cap App) in Children

VERSION DATE: 10/27/2022

amount of time required for the index finger color to return to its pre-compressed color. The measurement will be annotated by a trained human from the video recording by measuring the CRT with a stopwatch, as is the current standard.

- Computer annotation from manual CRT measurement: The same video from the manual CRT measurement will be used for the computer annotation. A research team member will manually select a section of the finger for use in the analysis and then a computer will analyze the color using signal processing. This annotation will serve as the gold standard of what is possible for human visual CRT measurement.

Individually Identifiable Health Information: Electronic data collection forms will be used to collect all relevant variables to help interpret CRT measurements in the context of the healthy patient populations. In brief, the following is the information that will be collected:

1) For healthy participants:

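### Skin temperature, a factor named in the secondary objectives, has no analysis relating it to Cap App CRT, and the Cap App versus manual comparison is not broken down by skin tone despite the pilot's warning

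*Combined protocol and SAP*

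**What the plan says.** The pilot in 2.1 (19 adults, unpublished) gives two warnings about the device, neither with an effect size. On skin tone: "It tends to overestimate CRT for darker skin tones". On temperature: "The results show that Cap App measures a longer CRT with greater variance in relation to the colder temperatures".

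The primary endpoint in 3.1 is "Determining the accuracy and precision of a mobile health application (Cap App) to measure CRT". Section 3.2 sets out to "determine if subject characteristics such as skin tone, skin temperature, sex, or age affect the CRT measured via the Cap App". It also asks for the correlation of Cap App with manual CRT, by age range only.

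The data needed are collected. Section 4.0 records "skin tone using the Fitzpatrick skin color scale", and 5.1 lists finger skin temperature, age and gender.

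The analysis text provides the following:

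- 10.1: an attempt to match participants on age group and skin tone at recruitment.
- 15.1: a within-subject comparison of manual and Cap App CRT, with no statistic and no subgroup named; Cap App normal ranges by age, sex and race (skin tone); room, core and skin temperature included only as a description.
- 15.3: mean CRT with 95% confidence intervals, overall and by age group, sex and skin tone, without saying which method is meant. ICCs and Bland–Altman plots are assigned to inter-rater reliability of the annotations.

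**The concern.** There are two separate gaps.

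The first is a mismatch between an objective and the analysis. Describing skin temperature reports how warm the fingers were. It does not show whether temperature affects the reading. If the plan is followed as written, one of the four factors named in 3.2 goes unanswered, and it is one for which the sponsor's own pilot saw an effect.

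The second concerns accuracy. Over-reading is a statement about one method relative to another, so a Cap App mean or range by skin tone cannot test it. If the device does read long in darker skin, a skin-tone-specific normal range would absorb that error as if it were normal physiology. Section 2.2 says the norms are meant to support later detection of perfusion abnormalities, so the error could carry forward.

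**Working it through.** **1. Trace each factor in 3.2 to an analysis.**

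| Factor | 15.1 | 15.3 |
|---|---|---|
| Age | Cap App range | Mean with CI |
| Sex | Cap App range | Mean with CI |
| Skin tone | Cap App range (under race) | Mean with CI |
| Skin temperature | Description only | Not mentioned |

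Skin temperature is the only factor with no CRT summary attached to it.

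**2. Reproduce the plan's precision.** Inputs from 15.3: SD 0.663 s, 48 per age group, 240 in total. Half-width = 1.96 × SD / √n.

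- n = 48: 1.96 × 0.663 / √48 = 0.188 s
- n = 240: 1.96 × 0.663 / √240 = 0.084 s

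Both match. They describe a single mean, by age group or overall. They do not cover a difference between methods or any skin-tone group, and the documents set no number per skin-tone group.

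**3. What a mean by skin tone can show.** Suppose, for illustration only, a shift of 0.25 s in one skin-tone group. The between-group contrasts (s) would be:

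| Cause | Cap App | Video | Cap App minus video |
|---|---|---|---|
| Cap App over-reads | 0.25 | 0 | 0.25 |
| Shared physiology | 0.25 | 0.25 | 0 |
| Video under-reads | 0 | −0.25 | 0.25 |
| Physiology plus video under-reading | 0.25 | 0 | 0.25 |

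The Cap App contrast is identical in the first two rows, while the paired contrast separates them. The paired contrast does not separate rows 1, 3 and 4, so it shows a relative difference and not which method is at fault.

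**4. Precision of a paired skin-tone analysis.** Assumptions not in the documents: SD 0.663 s for each method (15.3 does not say which method it describes), one reading each, between-method correlation ρ of 0.3, 0.5 or 0.7, and the group sizes.

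- SD of the difference, SDd = 0.663 × √(2(1 − ρ)) = 0.784, 0.663, 0.514 s.
- Half-width of the contrast between groups = 1.96 × SDd × √(1/n₁ + 1/n₂).
- Half-width of each limit of agreement = 1.96 × SDd × √(1/n + 1.96²/(2(n − 1))), with n the size of the smaller group.

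| Groups | Contrast, ρ = 0.3 / 0.5 / 0.7 | Limit of agreement in smaller group |
|---|---|---|
| 48 vs 192 | 0.248 / 0.210 / 0.162 s | 0.382 / 0.323 / 0.250 s |
| 24 vs 216 | 0.331 / 0.280 / 0.217 s | 0.544 / 0.460 / 0.356 s |
| 12 vs 228 | 0.455 / 0.385 / 0.298 s | 0.78 / 0.66 / 0.51 s |

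**5. Temperature slope, as an illustration.** Half-width = 1.96 × 0.663 / (SDtemp × √240). For an assumed finger-temperature SD of 1, 2 or 3 °C this is 0.084, 0.042 or 0.028 s per °C. It ignores adjustment for the other terms and uses the SD at normal hand temperature. The pilot reports greater variance in the cold, so the figures may be optimistic.

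**The case against.** The strongest reply is that no endpoint asks for agreement by skin tone. Section 3.2 asks whether skin tone affects Cap App CRT, which means and ranges by skin tone address descriptively, and it asks for correlation with manual CRT only by age range. This stands: the skin-tone breakdown extends the accuracy endpoint and is not a broken promise. The more basic omission is that 15.1 names no agreement statistic at all, and the breakdown belongs inside that analysis.

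It is also fair that the pilot signal is thin (19 adults, no effect size) and that 10.1 shows the sponsor had skin tone in mind. But matching is a recruitment step and tests nothing.

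The reference is imperfect too. For the computer annotation "a computer will analyze the color using signal processing", so it may itself depend on skin tone. It comes from a separate compression, with the hand "with their hand raised slightly above the level of the heart on a table" for the video and, for Cap App, "their hand resting on a table top in a resting position". This limits what a paired difference can prove, but 5.1 still makes that annotation the study's gold standard.

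I find no answer in the documents on skin temperature. That the study is descriptive and has no power calculation does not help, because no descriptive link between temperature and CRT is planned either.

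**Conclusion.** Both gaps are real. The temperature gap is the firmer one: a named objective has no analysis. The skin-tone gap is a worthwhile addition in support of the primary endpoint, prompted by the sponsor's own pilot. Neither invalidates the planned summaries.

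A reader might infer more than the documents support:

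- *That skin tone is not analysed.* It is, by mean CRT and by Cap App range. What is missing is the comparison between methods.
- *That the sponsor would compare the methods as independent samples and lose precision.* Section 15.1 places the comparison within each subject, and nothing proposes an unpaired analysis.
- *That the planned sample is known to be enough for the temperature question.* That would need an effect size and the spread of finger temperature. The pilot gives no effect size, and its 20 to 30 °C conditions were set with an ice bath, which this study does not use. The slope half-widths above are illustrations only.
- *That a paired difference would prove Cap App biased.* It is relative to the video reference.

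The precision figures rest on the assumed SD for each method, single readings, correlations and group sizes. With as few as 12 children in a skin-tone group, each limit of agreement would be known only to about ±0.78 to ±0.51 s, comparable to the SD itself.

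**What to change.** Add to 15.3:

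- (a) A model of Cap App CRT on continuous finger skin temperature, Fitzpatrick skin tone, age and sex, with a random child effect for repeat readings. Report the temperature slope and the adjusted effects with 95% CIs beside the unadjusted means.
- (b) Within the overall agreement analysis of Cap App against computer annotation, a model of the within-child difference on the same terms. Report the mean difference with 95% CI and the limits of agreement, overall and by skin tone. Describe the results as relative to the video reference, not as showing which method is biased. Pair by hand as well if hand was logged; the data list in 5.1 does not name it.
- (c) A statement of which method or methods the mean CRT refers to.

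The cost is SAP wording and modest extra modelling, with no new measurements or participants. The drawback is imprecision in small skin-tone groups, so group sizes and intervals should be shown. The recruitment window in 8.3 precedes this version's date, so the change should be dated and recorded before the Cap App readings are analysed.
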